FibroScan is available and has been shown to detect advancing levels of fibrosis, and it is clear that nonalcoholic fatty liver disease is increasing in prevalence throughout the western and developing worlds. Advancing liver disease leads to fibrosis, cirrhosis, and early death in a substantial portion of the population who could be helped with earlier lifestyle and medical interventions.

Vibrationcontrolled transient elastography (VCTE) is a point-of-service non-invasive technology that measures tissue elasticity and steatosis and can identify individuals at risk for disease progression and may therefore serve as an effective screening tool to alter the natural history of this disease and improve outcomes.

Changing a foundational strategy, such as responding to symptoms of liver disease, which is the current recommendation, to one of proactively intervening by screening for asymptomatic disease carries a large cost burden and is difficult to accomplish.

Objectives

The goal of this screening study is to gather FibroScan data from the at-risk but undiagnosed population on a self-selection basis so that perceived incidence rates can be calculated and the economics of a single function screening service can be evaluated.

The objective is to develop evidence based information to determine if noninvasive screening of at risk, comorbid people is feasible with this modality.

Furthermore, a secondary objective is to educate all participants about liver disease, lifestyle, healthy diets, and the role of clinical trials as part of the Foundation's larger mission of being patient advocates.

The value and necessity of clinical trials for the development of effective therapies is not well understood by the public. A goal of the foundation is to provide information about the clinical trial process to screening participants. The information is of a general nature (examples are attached). No specific trials will be mentioned. The participants will also be offered the opportunity to receive additional general education about trials and provided with links to systems in which they can explore available trials should they wish to do so. That information is of a general nature and no specific trials will be promoted. Participation in the screening will not automatically enroll them in further education as that decision is post testing and opt-in.

Questions Posed by this Study:

- What population demographics justify routine screening on a cost benefit basis?

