- The de-identified, but self-described, chronic ailments will be used with the scan results to broadly identify cohorts that may benefit from screening for asymptomatic disease.
- What operating cost burden is required to sustain a mobile screening project and what is the minimum utilization required to justify it?
- The operating costs of the study will be captured in order to inform an analysis of the financial constraints for deployment of mobile screening systems into local underserved communities.
- What portion of the asymptomatic patients with advanced disease will be willing to learn about clinical trials?
- Analysis of the posttest behavior of participants by their enrolling to learn more about clinical trials will measure the efficacy of using this method to educate the at risk population about clinical trials and ultimately inform decisions about how trial participants may be recruited in the future.
- What portion of the patients take advantage of free online diet support?
- Lifestyle changes are challenging as it is difficult to engage patients in the weeks following any testing. Tracking of the number who take advantage of the follow-up support will help guide future efforts to develop educational materials.

Patient Selection Criteria

The screening will be available to adults who self-select and who meet the inclusion criteria. The project will stop at 3 months or 1,000 patients, whichever occurs first. The goal is to

examine whether a self-referral design can serve as a cost effective patient centered wellness screening model.

Who may participate

- Adults 18 and over
- Patients with no diagnosis of liver disease
- Patients with any of these self-identified chronic conditions
 - Type 2 diabetes
 - Metabolic syndrome
 - Cardiovascular disease
 - Pre Diabetes
 - Sleep apnea
 - Digestive disorders
 - Osteoporosis
 - Polycystic ovarian syndrome
 - Psoriasis

Who may not participate

- Age less than 18
- Pregnant women
- Anyone with an implanted electronic device such as a defibrillator
- Morbidly obese, BMI 40 or greater
- Anyone not personally able to give informed consent
 - Non English speakers, no translator is available

Trial Candidate Outreach

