 - No fat but evidence of liver stiffness
 - Fat without liver stiffness
 - Fat with liver stiffness
 - Stiffness values indicative of cirrhosis
 - Stiffness values indicative of fibrosis without cirrhosis

NOTE: no individual follow up or track will be done as not personally identifiable information will be captured or retained.

2. The secondary goal is to determine factors that are statistically significantly associated with the presence or absence of fat with or without increased liver stiffness.

We will analyze data using a standard statistical software package, Stata® 12.1 (Stata Corp, College Station, TX). We will express continuous variables using the mean ± standard deviation, and we will test the null-hypothesis using the Student t-test. We will compare categorical variables using contingency table analysis. For all statistical tests, we will define a two-sided p-value of ≤0.05 as statistically significant. We will perform multivariate analysis of all risk factors found to be statically significant (p ≤0.05) using univariate analysis.

This exploratory goal seeks to determine the degree of satisfaction of subjects who undergo a screening CAP-FibroScan free of charge.

We will calculate the frequency of answers for each of the five items reflecting subjects' likelihood of:

- recommending this test to a friend or family member.
- sharing their results with their doctor.
- consulting with a liver specialist.
- seeking information about FDA-approved clinical trials of therapies for non-alcoholic fatty liver disease.
-

We will not perform statistical analyses for these descriptive data.

Disease Staging

The disease staging to be analyzed will be based upon these breakpoints from the FibroScan test. The test scores will be translated into these staging ranges for analysis.

Transient Elastography (TE):

Disease	F0-F1	F2	F3	F4
NAFLD/NASH	≤ 7.0	≤ 7.5	≤ 10.0	≤ 14.0

Reference: Current Gastroenterology Reports. 2014; 16: 372

TE Interpretation: The subject's liver stiffness score in kPa units shows:

- **F0:** No liver fibrosis
- **F1-2:** Mild-Moderate liver fibrosis
- **F3:** Severe liver fibrosis
- **F4:** Cirrhosis

Controlled Attenuation Parameter:

Steatosis Grade	% Steatosis on Liver Biopsy	CAP Value
Mild (S1)	5-33%	225-275 dB/M
Moderate (S2) to Severe (S3)	>33% >66%	275-400 dB/M

Reference: World J Gastroenterol. 2016; 22: 7236

DATA COLLECTION

Demographics:

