The data for analysis will be captured by these patient completed forms to provide demographic information, including sex, age, and race/ethnicity. We will measure height and weight prior to CAP/FibroScan testing.

Metabolic Syndrome:

Subjects will use a form to check YES or NO for comorbid components of the metabolic syndrome that they may or may not have:

- Obesity/overweight
- Diabetes mellitus
- Hypertension
- Hypercholesterolemia
- Hypertriglyceridemia
- Gout or elevated uric acid

Other Health Conditions:

Subjects will use a form to check YES or NO for other health conditions they may or may not have:

- Heart disease
- Heart attack
- Arrhythmia
- Stroke
- Arthritis
- Osteopenia/osteoporosis
- Hypothyroidism
- Low Vitamin D
- Low testosterone
- Menopausal state
- Inflammatory bowel disease (ulcerative colitis or Crohn's disease)
- Cancer
 - Skin: melanoma
 - Skin: basal cell or squamous cell cancers

- Other type of cancers: lymphoma; leukemia; head or neck; thyroid; brain; breast; lung; stomach; colon; liver; ovary; uterus; prostate; bone

Diet:

Subjects will fill out a form using a 5-point scale of the frequency of their average weekly dietary intake of specific food types: (A. 0 days, B. 1-2 days, C. 3-4 days, D. 5-6 days, E. 7 days per week)

- Proteins: eggs, cheese, beans, fish, chicken, turkey, beef, pork
- Starchy carbohydrates: breads, rolls, pasta, cereals, potatoes, rice, corn, peas, lima beans
- Non-starchy vegetables: lettuces, kale, carrots, green beans, broccoli, peppers, onions, cucumber
- Fats: butter, margarine, avocado, oils (olive, safflower, cottonseed, peanut, sesame, walnut)
- Nuts: peanuts, walnuts, cashews, almonds, macadamias, peanuts
- Sugars or Syrups: sugar, high fructose corn syrup (sodas), maple or corn syrups
- Fast food meals
- Eating out at restaurants

Exercise:

Subjects will fill out a form using a 5-point scale of the frequency of their average weekly exercise:

- (A. 0 days, B. 1-2 days, C. 3-4 days, D. 5-6 days, E. 7 days per week)
- Cardiovascular: brisk walking, jogging, biking, treadmill, stationary bike, stair stepper, elliptical, swimming laps
 - Strength: weight lifting, resistance machines or cords

Alcohol:

Subjects will fill out a form quantifying their average weekly total of alcoholic drinks:

(1 drink= 12 oz. beer, 6 oz. wine, 1.5 oz. hard liquor; 3 oz. brandy, sherry, liqueur):

- None
- 1-2 drinks/week
- 3-4 drinks/week
- 5-6 drinks/week
- 7-8 drinks/week
- 9-10 drinks/week

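### Entry requires one of nine conditions, so the planned Yes/No tests of those conditions lack a condition-free reference and give odds ratios shifted downward by an amount the plan cannot determine

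*Combined protocol and SAP*

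**What the plan says.** The protocol (Patient Selection Criteria) states: "The screening will be available to adults who self-select and who meet the inclusion criteria". The criteria admit "Patients with any of these self-identified chronic conditions": type 2 diabetes, metabolic syndrome, cardiovascular disease, pre-diabetes, sleep apnea, digestive disorders, osteoporosis, polycystic ovarian syndrome (PCOS) and psoriasis. Nobody without a listed condition is scanned.

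The first of the protocol's Questions Posed is "What population demographics justify routine screening on a cost benefit basis". To answer it, the self-described "chronic ailments will be used with the scan results to broadly identify cohorts that may benefit from screening for asymptomatic disease".

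The SAP's secondary goal (Data Analysis, item 2) is to "determine factors that are statistically significantly associated with the presence or absence of fat with or without increased liver stiffness". Categorical factors are compared by contingency table at two-sided p≤0.05, and only factors significant there enter a multivariate analysis.

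For exposures, the Data Collection sections state: "Subjects will use a form to check YES or NO for other health conditions they may or may not have". The printed items cover diabetes mellitus, heart disease and heart attack, osteopenia/osteoporosis, inflammatory bowel disease (IBD) and components of the metabolic syndrome. They have no item for pre-diabetes, sleep apnea, PCOS, psoriasis or digestive disorders other than IBD.

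The SAP's primary outcome section describes the sample as an at-large, self-selected population and does not mention the condition requirement.

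**The concern.** In an ordinary cross-sectional comparison, the No group for osteoporosis includes people with no relevant illness. Here it cannot: every participant without osteoporosis entered through another listed condition, and several of those, such as diabetes and metabolic syndrome, are expected to raise liver fat. The contingency table therefore compares osteoporosis with a mixture of other entry conditions, while its result would be read as the effect of having osteoporosis.

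The choice of cohorts for screening is at stake. A condition with a real but modest effect could fail the univariate test and be dropped, or an unrelated condition could be reported as protective. Data are anonymous and no individual is followed up, so an entry condition not recorded at intake probably cannot be recovered later.

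**Working it through.** **The plan's own figure.** The protocol gives a minimum of 400 participants for power of around 0.8, with no effect size, SD or hypothesis, so the figure cannot be confirmed or refuted. For two groups of 200 it implies (1.96 + 0.84) × √(1/200 + 1/200) = 0.28 SD. Nothing below depends on it.

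**Direction of the shift.** Take one entry condition. Everyone who has it is eligible, so the entry rule leaves the Yes group's risk unchanged. In the No group the rule removes people with no listed condition:

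risk(No, eligible) = [risk(No) − q × r0] / (1 − q)

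Here q is the share of the No group with no listed condition and r0 is the risk in those people. If r0 is below risk(No), the eligible No group's risk rises and the odds ratio falls, whether or not conditions cluster. If the condition is the only risk factor, risk(No) = r0 and nothing changes.

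**Assumed inputs** (the documents give none):
- Prevalences 12, 20, 10, 15, 12, 15, 8, 4 and 3%, in the protocol's order.
- Risk of fat with no listed condition: 25%.
- Odds ratios: diabetes 3, metabolic syndrome 3, cardiovascular disease (CVD) 1.5, pre-diabetes 2, sleep apnea 2, the other four 1.

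**Worked case: osteoporosis, independent conditions.**
- Share with no listed condition = 0.88 × 0.80 × 0.90 × 0.85 × 0.88 × 0.85 × 0.92 × 0.96 × 0.97 = 0.345.
- q = 0.345 / 0.92 = 0.375.
- Risk averaged over all combinations of conditions = 0.380. As osteoporosis is harmless here, this is the risk with or without it before the entry rule.
- Eligible No group: (0.3804 − 0.3751 × 0.25) / 0.6249 = 0.459.
- Odds ratio = (0.3804/0.6196) / (0.4587/0.5413) = 0.72, against a true 1.0.
- Share with osteoporosis among the eligible = 0.08 / 0.655 = 0.122, or about 49 of 400 and 122 of 1,000.
- SE of the difference = √(0.3804 × 0.6196/48.8 + 0.4587 × 0.5413/351.2) = 0.074 at 400, and 0.047 at 1,000.
- z = 0.0783/0.0744 = 1.05 and 0.0783/0.0471 = 1.66. The chance of a significant protective result is Φ(1.05 − 1.96) = 18% and Φ(1.66 − 1.96) = 38%.

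A second set of assumed inputs (osteoporosis prevalence 10%, PCOS also a risk factor) gives an odds ratio of 0.72, and 22% and 45%.

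**Effect of clustering.** Crude odds ratios without → with the entry rule, from 3,000,000 simulated people (latent correlation 0.3 where clustered; simulation differs from the hand arithmetic by about 0.01):

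| Condition (assumed OR) | Independent | Five metabolic/cardiovascular conditions clustered | All nine clustered |
|---|---|---|---|
| Diabetes (3) | 2.78 → 2.11 | 4.05 → 2.92 | 4.05 → 2.57 |
| CVD (1.5) | 1.45 → 1.06 | 2.37 → 1.63 | 2.37 → 1.41 |
| Digestive (1) | 1.00 → 0.70 | 1.00 → 0.61–0.68* | 1.67 → 0.92 |
| Osteoporosis (1) | 1.00 → 0.73 | 1.00 → 0.61–0.68* | 1.80 → 1.06 |
| Psoriasis (1) | 1.00 → 0.74 | 1.00 → 0.61–0.68* | 2.02 → 1.22 |

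*Range over the four harmless conditions.

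If only diabetes carries risk, its odds ratio is unchanged (3.01 → 3.01) and the harmless ones are 0.89–0.92. If no condition carries risk, there is no shift.

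**The planned multivariate step.** The gated procedure was run 1,000 times per setting. It generously treats metabolic syndrome as captured by its components and digestive disorders as fully recorded, although the form has only IBD. The harmless digestive condition was significantly protective as follows (univariate → after the multivariate step):
- Independent: 34% → 15% at 400; 65% → 25% at 1,000.
- Five clustered: 54% → 10%; 90% → 22.5%.
- All nine clustered: 5.2% → 2.4%; 8.5% → 3.4%.

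CVD passed the univariate gate in 6–7% of independent-case runs at either size. With the five clustered it passed in 42% and 80%, and with all nine clustered in 25% and 60%.

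**Which model repairs it** (independent case):
- All nine conditions, ungated: 3.02, 3.02, 1.50, 2.00 and 2.03 for the risk factors, 0.98–1.01 for the harmless ones. Clustered cases are equally close.
- Diabetes, CVD, digestive and osteoporosis only: 2.04, 1.07, 0.73 and 0.74.
- Those four plus metabolic syndrome: diabetes 2.39, metabolic syndrome 2.36, CVD 1.22, digestive 0.83, osteoporosis 0.82.

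**The case against.** The strongest reply concerns the target. The protocol is about at-risk, comorbid people, and among them a lower proportion with fat in osteoporosis than in other participants is a true and useful description. It is biased only against a causal or general-population odds ratio, which the documents do not claim. That stands for the proportions themselves. It only partly answers the point, because the SAP looks for risk factors by significance test and the protocol uses the conditions to choose cohorts; a contrast with a mixture of other entry conditions does not show whether a condition merits screening.

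A reader might go further and infer that the entry rule generally makes harmless conditions look protective and pulls real risk factors to 1. The documents do not support that. They give no prevalences, effects or correlations, and independence is implausible for a list that includes diabetes, pre-diabetes and metabolic syndrome. When all nine cluster, confounding pushes upward and a harmless condition can end near or above 1.

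A reader might also infer that all nine conditions are tested. They are not: the printed forms have items for only some, and the match is approximate (osteopenia with osteoporosis, IBD for digestive disorders). Protocol Step 2 mentions a list of comorbidities, but the lists printed in the protocol and SAP lack the missing conditions.

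Finally, the multivariate step is a real safeguard and lowers the false-signal rate. It is incomplete because it is gated on the same univariate tests and lacks some entry conditions.

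**Conclusion.** The point holds as a limitation of the secondary, association analysis. For the entry conditions that the form records, the No group qualified through a listed condition and is not condition-free. When the other conditions raise liver risk, the crude odds ratio is lower than it would be without the entry rule.

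That downward shift follows from the entry rule and the protocol's premise. Where the odds ratio ends up does not: harmless conditions range from about 0.61 to 1.22 across the settings examined, and CVD with an assumed odds ratio of 1.5 ranges from 1.06 to 1.63. Where a distortion from 1 exists, a larger sample makes a false signal more likely. All magnitudes rest on assumed prevalences, odds ratios and correlations.

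It would be wrong to infer that the primary proportions are distorted in this way. They are not, but they describe people with at least one listed condition, not an at-large population.

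**What to change.** 1. Add Yes/No items so that all nine entry conditions are recorded at intake. Step 1 already reviews the inclusion rules, so the answers need only be carried into the dataset.
2. For associations, enter all nine together in one model regardless of univariate p, in place of the univariate gate for these items.
3. For the first study question, report the proportion with fat, with stiffness and with F3–F4, with confidence intervals, in people with each condition. Report the same proportions descriptively in those for whom it is the only entry condition.
4. State that associations apply among people with at least one listed condition and that no condition-free group was scanned. Replace the at-large description in the SAP.

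Cost: a few form items, one table, one model and a short statement; eligibility and recruitment do not change. The single-condition cells will be small, and the joint model assumes no strong interactions. The form change must be in place before participants are seen.

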The primary patient outreach efforts will be to focus on high risk comorbid patients. We will communicate with local physicians to inform them that the service exists and invite them to refer appropriate patients to the screening facility or alternatively invite us to visit their offices with a portable unit.

The Foundation will also perform educational outreach through social media, communication through internet advertising, online forums, interaction with local support groups, media interviews and other educational efforts emphasizing the problem of our growing societal health crisis with obesity in general and liver disease in particular.

It is important to emphasize that during this study the FibroScan test will be free to qualified patients but they will be interviewed to ask what price they would be willing to pay on a private pay basis. This information will be used to perform the analysis of the viability of a private pay model. There will be no insurance or third party payment. Following testing the patient will be asked what payment amount, ranging from zero to more than \$400, would seem fair to them as a charge. The goal is to develop perceived value measures which can inform the financial modeling for the development of the fully deployed business plan.

Outputs of the project for the patient

All patients will receive education about liver disease as part of the intake process. Following the test, the patient will receive a printed output from their FibroScan test and instructions about next steps. Interpretation of test results require professional medical knowledge which is not provided by the study. Patients will be directed to a telemedicine system where they can discuss their results with professional staff and determine any next steps. Patients may elect to confer with their personal physician instead as is their right. Patients with test results indicating no active disease will be offered connections to nutrition and dietary support. In all cases patients will be offered enrollment in online educational tools about diet and lifestyle.

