- When any questions have been answered, the staff member will explain consent, provide the patient with the document, and answer any other questions.
- Upon signing of the consent the staff member will assign a random number to the consent and to the patient questionnaire.

Step 2: Data Capture

- After signing the consent form the patient will be asked to fill out the demographic form which will record basic health information, height, weight, sex, age, ethnicity, and identify any comorbid conditions of which they are aware from a list of common liver related comorbidities.

Step 3: The FibroScan test

- The patient will take the completed intake form and the educational materials with them to the FibroScan test room where the test will be performed.
- A certified FibroScan technician will double check the intake form and answer any additional questions that the patient may have.
- The technician will then administer the test according to the established standard test procedure and will identify it with the random number assigned to this test in step 1.

Step 4: Posttest process and instructions

- When the test is complete the test results will be printed out and given to the patient.
- The patient will also be given detailed information about how FibroScan is used and what it measures in a format that they can use to inform themselves so that they can better discuss the results and next steps with a physician. This will include explanations of how liver stiffness and fatty infiltration are defined and measured by the device.
- The patient will be asked to assess their perception of the value of the test to them personally by indicating what they perceive the value is of the test to them personally on a scale from nothing to over \$400.
- The patient will also be given printed information providing ways to contact resources and information about lifestyle changes, free support services, and information about how to access additional online tools.
- Most importantly, the patient will be instructed on how to access telemedicine support for interpretation of the test results and next steps. The technician will explain that the study provides the test, but interpretation must be done by a physician. Some patients may elect to discuss it with their existing doctor but

they will be encouraged to utilize the hepatology services, particularly if their test results are elevated.

Confidentiality

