 - The discussion provided useful information about FDA-approved clinical trials of therapies.
 - The discussion of my liver health will help me obtain better health care for my liver.
- b. If you answered dissatisfied or very dissatisfied, please check all the reasons for your answer:
- I do not understand what the CAP-FibroScan measures.
 - I do not understand how much fat I have within my liver.
 - I am not sure if I have or do not have scarring (fibrosis) of my liver.
 - The results did not give me a better understanding of my liver health.
 - The discussion did provide useful information about FDA-approved clinical trials of therapies.
 - The discussion of my liver health is unlikely to help me obtain better health care for my liver.

SUNN STUDY

STATISTICAL ANALYSIS PLAN

PRIMARY OUTCOME MEASURE – DETERMINE THE INCIDENCE AND STAGING OF UNDIAGNOSED NAFLD AND NASH IN A HEALTH CONSCIOUS SELF SELECTED POPULATION AS MEASURED WITH A FIBROSCAN

The study will measure the incidence and severity of the fat content and liver stiffness in an at large, self selected population who do not, at the time of testing, have a diagnosis of NAFLD, NASH or other liver disease. This will measure the incidence of undiagnosed liver disease and the statistical distribution of the disease staging in this population.

A key secondary outcome measure will be the incidence and disease distribution as a function of ethnicity.

We will analyze data using a standard statistical software package, Stata® 12.1 (Stata Corp, College Station, TX). We will express continuous variables using the mean \pm standard deviation, and we will test the null-hypothesis using the Student t-test. We will compare categorical variables using contingency table analysis. For all statistical tests, we will define a two-sided p-value of ≤ 0.05 as statistically significant. We will perform multivariate analysis of all risk factors found to be statically significant ($p \leq 0.05$) using univariate analysis.

Data Analysis

We will record all data in a Microsoft Excel worksheet. We will sequentially number each participating subject. We will not record any identifying information (e.g., names, initials, DOB, SSN, insurance, EPIC MRNs) in the database. Thus, all data assessments will maintain the anonymity of all participating subjects.

1. The primary goal is to calculate the proportion of men and women that when tested have CAP-FibroScan evidence of:
 - No fat or liver stiffness

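### Physician-referred and office-visit patients are pooled with self-referred ones, and no listed data item records the route, so the results cannot be attributed to self-referral

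*Combined protocol and SAP*

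**What the plan says.** **Goal.** Protocol, Patient Selection Criteria: the goal is to "examine whether a self-referral design can serve as a cost effective patient centered wellness screening model". The access rule in the same section reads "The screening will be available to adults who self-select and who meet the inclusion criteria". Under Objectives, the study is to "gather FibroScan data from the at-risk but undiagnosed population on a self-selection basis so that perceived incidence rates can be calculated".

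**Routes of entry.** Protocol, Trial Candidate Outreach: local physicians are named first. The study will tell them about the service and "invite them to refer appropriate patients to the screening facility or alternatively invite us to visit their offices with a portable unit". Public outreach is then added: "The Foundation will also perform educational outreach through social media, communication through internet advertising, online forums, interaction with local support groups, media interviews". No quota or ceiling is given for any route.

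**Data items.** Protocol, Step 2 (Data Capture), describes "the demographic form which will record basic health information, height, weight, sex, age, ethnicity, and identify any comorbid conditions of which they are aware". SAP, Data Collection, states: "The data for analysis will be captured by these patient completed forms to provide demographic information, including sex, age, and race/ethnicity". The remaining listed items cover metabolic syndrome, other conditions, diet, exercise, alcohol, other liver diseases, the perceived price, and the experience and satisfaction survey. None of them is a referral source or a scan site.

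**Analysis.** SAP, Primary Outcome Measure, describes measurement "in an at large, self selected population". Under Data Analysis, the primary proportions are taken over all men and women tested. Ethnicity is the named key secondary breakdown, and route does not appear.

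**The concern.** Someone who answers an advertisement and someone whom a physician judged suitable for a scan enter by different mechanisms. Disease yield, stated price and intention to follow up may differ between them. The protocol means to use its results for a private-pay business plan, for deploying mobile screening, and in support of a change in professional guidance. Each use depends on knowing which way of recruiting produced the figures.

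If the plan is followed as written, one pooled set of proportions and price answers results, with no listed item by which to divide it. A reader could credit the pooled yield to self-referral when an unknown part came through physicians. Because the SAP also rules out individual follow-up and keeps no identifiers, the plan describes no way to go back to participants for the missing item.

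**Working it through.** The plan has no figure of its own on this point. Its only design figure is a minimum of 400 participants for a power of about 0.8 (protocol, Intended Use of the Data). No effect size or comparison accompanies that figure, so it cannot be reproduced. The argument below does not depend on it.

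1. **Inputs.** From the documents: sample size 400 to 1,000. Assumed, because the documents give no values: *s*, the share entering by either physician route; *p_self*, the rate of a finding among the self-referred; *p_ref*, the rate among the rest.

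2. **Pooled rate and bias.** Pooled = (1 − *s*) × *p_self* + *s* × *p_ref*. Subtracting *p_self* gives bias = *s* × (*p_ref* − *p_self*). The sample size does not enter.

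3. **Larger assumed gap.** With *p_self* = 10% and *p_ref* = 20% to 30%:
   - *s* = 10%: 0.9 × 10 + 0.1 × 20 = 11%, up to 0.9 × 10 + 0.1 × 30 = 12%.
   - *s* = 30%: 0.7 × 10 + 0.3 × 20 = 13%, up to 0.7 × 10 + 0.3 × 30 = 16%.
   - *s* = 50%: 0.5 × 10 + 0.5 × 20 = 15%, up to 0.5 × 10 + 0.5 × 30 = 20%.

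4. **Smaller assumed gap.** With *p_self* = 30%, *p_ref* = 35% and *s* = 10%, bias = 0.1 × (35 − 30) = 0.5 points. With the two rates exchanged, it is 0.1 × (30 − 35) = −0.5 points. The sign is therefore open too.

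5. **Effect of sample size.** Take *p_self* = 30%, *p_ref* = 40%, *s* = 25%. Pooled = 32.5%, bias = 2.5 points. Coverage of *p_self* by the pooled 95% interval is Φ(1.96 − b/SE) − Φ(−1.96 − b/SE), with SE = √(0.325 × 0.675 / n).
   - n = 400: SE = 2.34 points, coverage 81%.
   - n = 1,000: SE = 1.48 points, coverage 61%.

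   The larger sample narrows the interval around the wrong value for this purpose. In the case in step 4 (30% against 35%, share 10%), coverage at n = 400 is 94.5%, which is harmless.

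6. **Precision if the strata are separated.** Half-width = 1.96 × √(p(1 − p)/n). At p = 10%: 1.96 × √(0.09/400) = 2.9 points for 400 people, and 1.96 × √(0.09/280) = 3.5 points if 280 of the 400 are self-referred.

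**The case against.** The strongest reply is that a referred patient still chooses to come, books an appointment and consents, and so still self-selects. The term self-referral appears only in the goal sentence. The access rule, the objective and the SAP speak of self-selection. On this reading the mixed offer is the intended model, office visits with a portable unit suit the protocol's question about mobile screening, and pooling answers the SAP's primary goal. Most of this stands. A reader might infer that the SAP's description of its population contradicts the outreach plan. The documents do not support that, since self-selected can include referred. What remains is the goal sentence set against the outreach section.

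Four other tempting readings also go too far.

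- *Physician referral inflates the yield.* Every participant must already report a listed chronic condition, and a suitable referral may mean no more than meeting that criterion. Nothing in the documents gives a rate by route.
- *The routes can never be separated.* The intake form itself and the appointment records are not reproduced. The supportable statement is that route is not among the listed items.
- *The self-referred group should replace the pooled result as the main analysis.* That changes the target population, which the stated primary goal does not require.
- *Clustering at offices seriously affects the tests.* With an assumed 20 people per office and an assumed intra-site correlation of 0.01 to 0.05, the design effect is 1 + 19 × 0.01 = 1.19 to 1 + 19 × 0.05 = 1.95. It applies only to office-visit participants. If they were 30% of the sample, the pooled variance would rise by a factor of 1 + 0.3 × 0.19 = 1.06 to 1 + 0.3 × 0.95 = 1.29.

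The objection does not restore the ability to attribute results to self-referral. If the physician share is in fact negligible, only a route field would show it.

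**Conclusion.** The point holds in a limited form. The study can report prevalence, perceived value and total cost for a voluntary, free, mixed-route offer, and those results are valid for that mix. As the data items and analyses are listed, it cannot say what part of the yield or of the price answers belongs to self-referral, which is what the goal sentence asks.

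The distortion could be negligible (0.5 points) or substantial (a pooled 13-16% against a self-referred 10%), and it could run in either direction. All rates and shares behind these figures are assumptions. What does not rest on them is that the bias is independent of sample size and that the listed data would not reveal which case applies. The finding also assumes that the listed items are complete. The change should be made before enrolment starts.

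**What to change.** Reconcile the goal sentence in Patient Selection Criteria with Trial Candidate Outreach, and then:

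- Add to the intake form a coded route field (self / physician-referred / physician-office visit) and a coarse site code.
- State in the SAP that the primary proportions, the price answers (which the protocol collects but the SAP does not mention) and the survey frequencies are reported by route beside the pooled result. Conclusions about a self-referral model should come from the self-referred stratum.
- If office visits make up a material share, use site-clustered standard errors for the pooled estimate.
- Do not promise online-education uptake by route. The protocol (Intended Use of the Data) follows that response only in aggregate, so an intake field cannot be linked to it.

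The cost is two coded fields and a short SAP addition. Intervals for the self-referred stratum will be wider: 3.5 instead of 2.9 points in the example above, and more if few participants come by that route. Site codes must also be coarse enough, for instance by grouping small offices, that together with age, sex and ethnicity they do not weaken the assurance that participants cannot be identified. Very coarse codes would in turn limit the clustering adjustment.
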